3.1.1.4 Vital signs variables

Vital signs variables include weight, heart rate, blood pressure (systolic and diastolic), respiratory rate, and temperature will be assessed at every scheduled clinical visit. Highest and lowest daily temperature will be monitored as well. In addition, length will be collected at baseline only.

For heart rate and blood pressure measurements at baseline, at least 2 measurements will be taken during a 30 minute period; the mean of all measurements will be utilized for analysis.

3.1.1.5 Other safety variables

Other safety variables include:

- Physical exam by body system (general appearance, skin, head and neck, lymph nodes, musculoskeletal/extremities, cardiovascular, respiratory, abdomen, and neurological) through TOC, with specification of baseline and new/aggravated abnormalities
- Imaging study results (chest radiograph [CXR], computed tomography [CT] scan, or other radiology) through TOC including location, type of examination, result normal/abnormal, and description of abnormal findings
- Adjunctive therapeutic procedures related to infections variables through TOC including procedure, procedure type, other (specify), start date and time, stop date and time, and reason for procedure.

3.2 Secondary outcome variables

3.2.1 Efficacy variables

3.2.1.1 Clinical response variable at EOT and TOC

Efficacy outcome measures will include clinical response at EOT and TOC. The clinical outcome categories at EOT are defined in [Table 4](#) below and the clinical outcome categories at TOC as defined in [Table 5](#) below. A favourable outcome is clinical cure.

Table 4 Clinical outcome categories at End-of-Therapy

Outcome	Definition
Clinical Cure	Resolution of all acute signs and symptoms of LOS or improvement to such an extent that no further antibacterial therapy is required
Clinical Failure	Subjects who received ≥ 48 hours of study treatment and meet any of the following: 
 • Discontinuation of study therapy due to insufficient therapeutic effect, including persistence, incomplete clinical resolution, worsening in signs and symptoms of LOS, or isolation of a resistant pathogen that requires alternative nonstudy antibacterial therapy • Discontinuation of study therapy due to a study therapy-related AE and requirement for alternative nonstudy antibacterial therapy for LOS • Death in which LOS is contributory
Indeterminate	Study data are not available for evaluation of efficacy for any reason, including: 
 • Death in which LOS is clearly noncontributory • Lost to follow-up • Extenuating circumstances precluding classification as a cure or failure • Diagnosis of CNS infection, osteomyelitis, endocarditis, or NEC at any time after enrolment • Received < 48 hours of study therapy

Abbreviations: AE=adverse event; CNS=central nervous system; LOS=late-onset sepsis; NEC=necrotizing enterocolitis.

Table 5 Clinical outcome categories at Test-of-Cure

Outcome	Definition
Clinical Cure	Resolution of all acute signs and symptoms of LOS or improvement to such an extent that no further antibacterial therapy is required
Clinical Failure	Subjects who received ≥ 48 hours of study treatment and meet either of the following criteria: 
• Incomplete resolution or worsening of LOS signs or symptoms or development of new signs or symptoms, or isolation of a resistant pathogen requiring alternative nonstudy antibacterial therapy• Death in which LOS is contributory
Indeterminate	Study data are not available for evaluation of efficacy for any reason, including: 
• Death in which LOS is clearly noncontributory• Lost to follow-up• Extenuating circumstances precluding classification as a cure or failure• Diagnosis of CNS infection, osteomyelitis, endocarditis, or NEC at any time after enrolment• Received < 48 hours of study therapy

Abbreviations: CNS=central nervous system; LOS=late-onset sepsis; NEC=necrotizing enterocolitis.

Per-patient clinical response at TOC will be derived from clinical outcome (ie, investigator assessment) of clinical cure, clinical failure, or indeterminate at EOT and TOC as shown in Table 6 below.

Missing values may occur due to failure to record a response at TOC due to earlier clinical failure. An outcome of clinical failure at EOT will be carried forward to TOC. Missing values may occur due to premature discontinuation from study therapy administration. Patients who were prematurely discontinued from study therapy administration for any reason will have EOT assessments conducted (see [Section 1.2](#)) and will have per-patient clinical response at TOC derived according to the rules in [Table 6](#). Unrelated deaths will be assessed as indeterminate for all remaining scheduled clinical assessments. Deaths occurring after TOC will not retrospectively change the TOC outcome (ie, if a patient was a clinical cure at TOC but died after TOC their clinical response at TOC remains clinical cure).

Table 6 Derivation of clinical response at TOC

EOT Outcome	TOC Outcome	Clinical Response at TOC
Clinical Cure	Clinical Cure	Clinical Cure
	Clinical Failure	Clinical Failure
	Indeterminate	Indeterminate
	Missing	Indeterminate
Clinical Failure	Clinical Cure	Clinical Failure
	Clinical Failure	Clinical Failure
	Indeterminate	Clinical Failure
	Missing	Clinical Failure
Indeterminate	Clinical Cure	Clinical Cure
	Clinical Failure	Clinical Failure
	Indeterminate	Indeterminate
	Missing	Indeterminate

The proportion of MITT Analysis Set patients with a clinical cure will be defined using the following formula:

$$\frac{\text{Number of patients with clinical response at TOC} = \text{clinical cure}}{(\text{Number of patients with clinical cure} + \text{Number of patients with clinical failure} + \text{Number of patients with indeterminate})}$$

The proportion of MITT Analysis Set patients with clinical failure and with indeterminate clinical response will be calculated analogously. For proportion of patients with clinical cure, clinical failure, and indeterminate, indeterminate or missing assessments will be included in the denominator for calculation of the proportions for the MITT Analysis Set.

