The study design is described in the Study Diagram ([Figure 1](#)). Patient participation will require up to 49 days (up to 14 days of treatment plus up to 35 days of safety follow-up). The total duration of study therapy is 48 hours (minimum) to 14 days (maximum). Hospitalization is required during IV study therapy. Baseline assessments for study eligibility will occur within 36 hours before the first dose of study therapy.

Procedures will be performed according to the Study Plan in [Table 1](#). Safety assessments will be done throughout the study. Between Day 2 and Day 14, 2 blood samples will be collected for PK analysis. The efficacy of ceftaroline fosamil will be evaluated based on the clinical outcome (clinical cure, clinical failure or indeterminate) at end of therapy (EOT; within 24 hours after completion of last infusion) and test-of-cure (TOC; 8 to 15 days after the last dose of study therapy) assessments. The Safety Follow-up (SFU) assessments will occur 28 to 35 days after the last dose of study therapy. Adverse events (AEs) will be followed up in the study until SFU.

A patient who is prematurely discontinued from study therapy administration for any reason will have EOT assessments conducted and undergo subsequent safety assessments at TOC and SFU per protocol.

[figure not shown]
- If a patient is prematurely discontinued from study therapy due to an adverse event and the clinical signs and symptoms of sepsis have resolved completely or improved such that no further antibacterial therapy is necessary, the patient will be assessed as a clinical cure at EOT and reassessed at TOC.
- If a patient is prematurely discontinued from study therapy due to a study therapy-related AE and requires alternative non-study antibacterial for treatment for LOS, the patient will be assessed as a clinical failure (or indeterminate, if the patient discontinued before minimum treatment duration) at EOT and TOC.
- If a patient is prematurely discontinued from study therapy administration (at any time after the required minimum treatment duration of 48 hours) due to insufficient therapeutic effect, the patient will be assessed as a clinical failure on the day of discontinuation (ie, EOT) and at all subsequent evaluation time points.

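### SAP Table 6 can count an infant who was indeterminate at EOT and recovered on a non-study antibacterial as a clinical cure at TOC

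*SAP*

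**What the plan says.** SAP section 3.2.1.1 takes the TOC result from two investigator entries: "Per-patient clinical response at TOC will be derived from clinical outcome (ie, investigator assessment". Infants who stopped study therapy early, for any reason, "will have per-patient clinical response at TOC derived according to the rules in" Table 6. One row of that table reads "Indeterminate Clinical Cure Clinical Cure" (EOT outcome, TOC outcome, derived response). Only a failure at EOT is carried forward; an indeterminate EOT outcome is not.

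Tables 4 and 5 give Cure the same definition. It asks for resolution of signs and symptoms, or enough improvement that no more antibacterial treatment is needed. It sets no minimum duration and does not mention non-study antibacterials. Failure requires at least 48 hours of study treatment. Both tables list as Indeterminate "Received < 48 hours of study therapy" and "Diagnosis of CNS infection, osteomyelitis, endocarditis, or NEC at any time after enrolment".

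SAP section 1.2 adds rules by reason for stopping:
- For a study therapy-related AE with need for another antibacterial, "the patient will be assessed as a clinical failure (or indeterminate, if the patient discontinued before minimum treatment duration) at EOT and TOC".
- For an AE of any cause with sepsis resolved, the infant is a cure at EOT. No 48-hour condition is attached.
- The rule on lack of effect applies only "at any time after the required minimum treatment duration of 48 hours) due to insufficient therapeutic effect".

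**The concern.** The cure rate is meant to describe recovery on ceftaroline fosamil with ampicillin and the optional aminoglycoside. Table 6 shows that its authors saw the risk of a late recovery being credited wrongly, because a TOC cure after an EOT failure is forced to Failure. A TOC cure after an indeterminate EOT has no such guard. The derivation does not ask why EOT was indeterminate or what the infant received between EOT and TOC.

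A recovery produced by another antibacterial can therefore enter the numerator. Such an infant stays in the MITT set, which requires only some ceftaroline fosamil and the minimal LOS criteria, with no minimum duration. The sensitivity analysis in SAP section 4.2.7.1 drops only infants derived as indeterminate, so it would keep this one. Under SAP section 3.2.1.2, if there is no TOC culture, the baseline pathogen would also become presumed eradicated.

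**Working it through.** There is no plan figure to reproduce beyond the sample size, 3 × 8 = 24. The check follows infants through Tables 4, 5 and 6 and then sizes the effect.

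**Infant A: at least 48 hours of therapy, stopped for an AE not related to study therapy, LOS still needing treatment, switched to a non-study antibacterial, recovered by TOC.**

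| Step | Rule | Result |
|---|---|---|
| EOT, Cure? | More antibacterial therapy is needed | No |
| EOT, Failure? | Not stopped for lack of effect; AE not related; no death | No |
| EOT | What remains in Table 4 | Indeterminate |
| TOC, Failure? | No unresolved, worse or new signs; no resistant isolate; no death | No |
| TOC, Cure? | Signs resolved; no bar on non-study drugs | Yes |
| Table 6 | Indeterminate + Cure | Clinical Cure |

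The 48-hour bullet and the listed diagnoses in Table 5 do not apply to this infant. SAP section 1.2 and Protocol section 3.9.1.1 cover the need for another antibacterial only where the AE is related to study therapy.

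**Infant B: under 48 hours of therapy, EOT recorded as Indeterminate under Table 4.** The four Table 6 outputs are:
- TOC Cure gives Cure.
- TOC Failure gives Failure.
- TOC Indeterminate gives Indeterminate.
- TOC Missing gives Indeterminate.

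An investigator who applies Table 5 enters Indeterminate, and the result is Indeterminate. A cure arises only if Cure is entered despite the 48-hour bullet. A recovered infant also meets the wording of Cure, and neither table says which category wins. The same reasoning holds for a later CNS infection, osteomyelitis, endocarditis or NEC diagnosis.

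**Infant C: under 48 hours, stopped for an AE, sepsis resolved.** Protocol section 3.9.1.1 and SAP section 1.2 call this cure at EOT; Table 4 calls it Indeterminate. If Cure is entered at both visits, Table 6 returns Cure through a different row.

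**Scale.** The change per affected infant is 1/n: 1/24 = 4.2 points overall and 1/8 = 12.5 points in a cohort. The documents give no expected cure count, so the counts below are assumptions. Intervals are Jeffreys 95%, the quantiles of Beta(x + 0.5, n − x + 0.5).

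| Assumed derived cures | As planned | One infant moved to Indeterminate |
|---|---|---|
| 16/24 | 66.7% (46.8 to 82.8) | 15/24 = 62.5% (42.6 to 79.6) |
| 20/24 | 83.3% (65.1 to 94.1) | 19/24 = 79.2% (60.2 to 91.6) |
| 22/24 | 91.7% (75.9 to 98.2) | 21/24 = 87.5% (70.3 to 96.4) |
| 7/8 (one cohort) | 87.5% (54.6 to 98.6) | 6/8 = 75.0% (40.8 to 94.4) |

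With two such infants, 20/24 becomes 18/24 = 75.0% (55.5 to 88.8).

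For the analysis excluding indeterminates, take 20/24 with all other infants failures. As planned, it stays at 20/24 = 83.3%. With the infant reclassified it is 19/23 = 82.6% (63.8 to 93.8).

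**The case against.** The strongest reply is that the plan, read whole, already deals with the obvious cases. Table 5 defines the TOC entry that feeds Table 6, and it lists both short therapy and the named diagnoses as Indeterminate. With those entries Table 6 returns Indeterminate, which agrees with SAP section 1.2. This stands. A reader might infer that Table 6 contradicts section 1.2 and turns infants switched before 48 hours into cures. The documents do not support that. It takes a TOC entry of Cure against Table 5, and section 1.2 fixes Indeterminate at both visits only for study therapy-related AEs.

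A reader might also infer that entry errors could only raise the cure rate, because Failure needs 48 hours. That does not follow either. Protocol section 3.9.1.1 assigns failure to the related-AE case with no exception for short therapy, so an unchecked entry could go the other way.

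For Infant A, two replies are available. Table 5 allows Indeterminate for extenuating circumstances, and Protocol section 7.7 bars other antibacterials except after clinical failure. The first applies when classification as cure or failure is precluded, whereas Infant A meets the Cure wording at TOC. The second is a treatment restriction; it assigns no outcome category.

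It is also fair that outcomes, ceftaroline fosamil exposure and medications are listed by patient and reviewed before lock, so a careful reader could spot such an infant. That makes a case visible but does not correct the tabulated rate.

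**Conclusion.** The concern holds as a gap in the derivation. Table 6 can credit study therapy with a recovery on a non-study antibacterial, and the clearest route is the infant with at least 48 hours of therapy stopped for an unrelated AE, where Table 5 offers no specific stop. For short therapy and the listed diagnoses the classification is already stated; what is missing is its precedence over Cure and any enforcement in the derivation.

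The row as a whole is not wrong. A TOC cure after an EOT that was indeterminate for some other reason, such as extenuating circumstances, is a proper use of it.

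The size is 4.2 points overall or 12.5 points in a cohort per affected infant, assuming the MITT set has the planned 24 and 8. It could be smaller than planned, and then each infant weighs more. The number affected is unknown and may be zero. The endpoint is secondary and descriptive with no hypothesis test, so this should be corrected but does not touch the primary safety objective.

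**What to change.** 1. State in SAP section 3.2.1.1 that the Indeterminate criteria of Table 5 take precedence over Cure.
2. Add a rule to Table 6. When EOT is Indeterminate and TOC is recorded as Cure, the derived response is Indeterminate if the infant received under 48 hours of study therapy, had a CNS infection, osteomyelitis, endocarditis or NEC diagnosis after enrolment, or received a non-study antibacterial for LOS before TOC.
3. Leave a TOC entry of Failure unchanged. A rule that applied whatever the TOC entry would erase valid failures, for example a resistant pathogen that needed other therapy.
4. Keep the Indeterminate + Cure row for all other reasons.
5. Reconcile Protocol section 3.9.1.1 with SAP section 1.2 and Tables 4 and 5. They differ on failure before 48 hours in the related-AE case, and on cure at EOT before 48 hours when sepsis has resolved. The Table 6 rule does not reach an infant entered as Cure at EOT, so this step is needed as well.

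The cost is a short derivation rule and one sentence. Infusion dates and times (Protocol section 7.5) and all antimicrobials (Protocol section 7.7) are already recorded. Whether the medication record shows that an antibacterial was given for LOS is an assumption to confirm. The investigator's own category should still be listed beside the derived one. The downside is that the reported cure rate may fall slightly.

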3.2.1.2 Per-pathogen and per-patient microbiological response variables at EOT and TOC

The per-pathogen microbiological outcome categories for pathogens identified at baseline are defined in [Table 7](#). Local microbiology data will only be used when central data is not available, for example, samples were not sent to the central laboratory for processing. Please see [section 3.3.1.3](#) for further details.

Table 7 Per-pathogen microbiological response categories

Microbiological Response ^a	Definition	Response Category
Eradication	Source specimen demonstrated absence of the original baseline pathogen	Favorable
Presumed eradication	Source specimen was not available to culture and the patient was assessed as a clinical cure	Favorable
Persistence	Source specimen demonstrates continued presence of the original baseline pathogen	Unfavorable
Presumed persistence	Source specimen was not available to culture and the patient was assessed as a clinical failure	Unfavorable
Indeterminate	Source specimen was not available to culture and the patient's clinical outcome was assessed as indeterminate	Indeterminate

^a For patients who were clinical failures before TOC, the microbiological outcome will be carried forward to TOC and will be determined based on the cultures and/or clinical outcome at the time of the early clinical failure determination.

Similarly, per-patient microbiological response will be categorized as favorable, unfavorable, or indeterminate as follows. Per-patient microbiological response at EOT and TOC will be derived programmatically based on individual outcomes for each baseline pathogen. In order for a patient to have a favorable per-patient microbiological response, the outcome for each baseline pathogen must be favorable (eradicated or presumed eradicated) at that time point. This includes results of blood cultures, urine cultures, CSF cultures or other specimen cultures at the time point. If the outcome for any baseline pathogen from any culture is unfavorable (persistence or presumed persistence) at that time point, the patient will be considered to have an unfavorable per-patient microbiological response. If there is an indeterminate per-pathogen microbiological response at the time point (ie, no culture result available and patient's clinical outcome was indeterminate), the patient will be considered to have an indeterminate per-patient microbiological response. For per-patient microbiological response at TOC visit, the above definition is only applicable to patients who are not clinical failures at EOT.

Patients who are clinical failures at EOT will have the corresponding per-patient microbiological outcome determined from EOT cultures and carried forward to TOC. If no EOT culture is available for patients who are clinical failures at EOT, then the microbiological outcome at TOC will be presumed persistence. Otherwise, the microbiological outcome at TOC will be determined from cultures obtained within the TOC visit window. If no culture is available in the TOC window, then the microbiological outcome at TOC will be presumed from the clinical response at TOC (if clinical cure, the microbiological outcome will be presumed eradication; if clinical failure, the microbiological outcome will be presumed persistence; if clinically indeterminate, the microbiological outcome will be indeterminate).

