4.3.1.3. Microbiological assessments

- If clinically indicated and performed as part of patient's regular medical care, obtain blood and urine samples for testing per [Section 5.2.1](#) and [5.2.2](#), respectively; cultures should be repeated per standard of care upon knowledge of a positive result until sterilization is confirmed
- If clinically indicated and performed as part of patient's regular medical care, obtain CSF or other specimens/tissue samples per [Section 5.2.3](#) and [5.2.4](#), respectively; cultures may be repeated per standard of care upon knowledge of a positive result.

If a patient was previously assessed as a clinical failure, perform only safety assessments (ie, AEs and SAEs, concomitant medications, weight, vital signs, CBC with differential, chemistry panel).

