8.4.2. Microbiological response definitions

8.4.2.1. Microbiological Outcome at Test-of-Cure

The per-pathogen microbiological outcome categories at EOT and TOC are defined in [Table 6](#). Favourable microbiological outcomes are eradication or presumed eradication. Per-patient microbiological response at EOT and TOC will be determined programmatically based on individual outcomes for each baseline pathogen. In order for a patient to have a favourable microbiological response, the outcome for each baseline pathogen must be favourable (eradicated or presumed eradicated). If the outcome for any pathogen is unfavourable (persistence or presumed persistence), the patient will be considered to have an unfavourable microbiological response.

Baseline pathogens will be determined based on central laboratory data. Rules for determination of pathogens will be described in the SAP.

Table 6 Per-pathogen microbiological outcomes categories at End of Treatment and Test-of-Cure

Microbiological Response ^a	Definition
Eradication	Source specimen demonstrated absence of the original baseline pathogen
Presumed eradication	Source specimen was not available to culture and the patient was assessed as a clinical cure
Persistence	Source specimen demonstrates continued presence of the original baseline pathogen
Presumed persistence	Source specimen was not available to culture and the patient was assessed as a clinical failure
Indeterminate	Source specimen was not available to culture and the patient's clinical outcome was assessed as indeterminate

a For patients who are clinical failures before TOC, the microbiological outcome will be carried forward to TOC and will be determined based on the cultures and/or clinical outcome at the time of the early clinical failure determination.

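### SAP 3.2.1.2 carries the microbiological outcome forward only for clinical failures at EOT, a narrower scope than Table 7 footnote a, so an infant who relapses and receives a rescue antibacterial before TOC can be scored as eradicated

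*SAP*

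**What the plan says.** Two statements in SAP 3.2.1.2 set the scope of carry-forward.

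- Footnote a to SAP Table 7: "For patients who were clinical failures before TOC, the microbiological outcome will be carried forward to TOC". The carried outcome rests on the cultures and/or the clinical outcome "at the time of the early clinical failure determination". Footnote a to Protocol Table 6 (section 8.4.2.1) has the same scope: "For patients who are clinical failures before TOC, the microbiological outcome will be carried forward to TOC".
- The derivation text below the table: "Patients who are clinical failures at EOT will have the corresponding per-patient microbiological outcome determined from EOT cultures and carried forward to TOC". For all other patients: "Otherwise, the microbiological outcome at TOC will be determined from cultures obtained within the TOC visit window". The fallback is: "If no culture is available in the TOC window, then the microbiological outcome at TOC will be presumed from the clinical response at TOC".

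The same section makes a patient unfavourable if any culture at the time point shows the baseline pathogen. SAP Table 6 makes an infant rated cure or indeterminate at EOT and failure at TOC a clinical failure at TOC. SAP 4.2.7.2 reports the favourable rate with a Jeffreys 95% interval, and also tabulates results by pathogen and by ceftaroline MIC.

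**The concern.** The footnotes cover every clinical failure before TOC. The derivation text covers only those at EOT. Between the two lies about a week: EOT falls within a day of the last infusion and the TOC window opens on day 8 after dosing ends. A culture taken at a relapse on, say, day 5 belongs to neither window, so the text never uses it.

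The protocol foresees events in that interval. Section 4.3.2 refers to clinical relapse, section 4 allows unplanned visits, section 5.2.1 allows blood cultures at any point up to TOC, and section 7.7 ties other antibacterials to clinical failure. For an infant with a positive culture, section 4.3.1.3 adds that "cultures should be repeated per standard of care upon knowledge of a positive result until sterilization is confirmed". A sterile culture obtained under a non-study drug can therefore fall in the TOC window, and the text would count it as eradication. Sterilisation by another drug would then be credited to study therapy in the microbiological tables, while the clinical table shows the same infant as a failure. Neither document says how a culture taken after a non-study antibacterial is to be scored.

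**Working it through.** The plan gives no figure to reproduce here. The study is descriptive, and its 24 patients (three cohorts of 8) rest on no alpha, power or effect size. The check has two parts.

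**1. The two rules side by side.** Take an infant who is not a failure at EOT, relapses before TOC, and has a TOC clinical response of failure. *Positive* means the baseline pathogen was grown. *Mixed* means both positive and sterile cultures in the window.

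| Culture at relapse | Cultures in TOC window | Derivation text | Footnote a, wider reading |
|---|---|---|---|
| Positive | Sterile only | **Eradication (favourable)** | **Persistence (unfavourable)** |
| Positive | Positive or mixed | Persistence | Persistence |
| Positive | None | Presumed persistence | Persistence |
| None | Sterile only | **Eradication (favourable)** | **Presumed persistence (unfavourable)** |
| None | Positive or mixed | Persistence | Presumed persistence |
| None | None | Presumed persistence | Presumed persistence |
| Sterile | Sterile only | Eradication | Eradication |
| Sterile | Positive or mixed | Persistence | Eradication |
| Sterile | None | Presumed persistence | Eradication |

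When the relapse culture is positive or absent, the text gives a favourable score in one of the four TOC-window patterns (sterile only, positive only, mixed, none). That is the pattern at issue. When the relapse culture is sterile, the rules can differ in the other direction.

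**2. Effect of one infant.** Shift = 1/n. The Jeffreys limits are the 2.5% and 97.5% points of Beta(x + 0.5, n − x + 0.5), with the upper limit set to 100% when x = n (a usual convention; the SAP does not state one). All other infants are taken as favourable for illustration.

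| n | Infant scored favourable | Infant scored unfavourable | Shift |
|---|---|---|---|
| 24 (all planned patients) | 24/24 = 100% (90.2–100) | 23/24 = 95.8% (82.1–99.5) | 1/24 = 4.2 points |
| 12 (assumed) | 12/12 = 100% (81.5–100) | 11/12 = 91.7% (67.2–99.1) | 1/12 = 8.3 points |
| 8 (one cohort) | 8/8 = 100% (73.8–100) | 7/8 = 87.5% (54.6–98.6) | 1/8 = 12.5 points |
| 4 (assumed) | 4/4 = 100% (55.5–100) | 3/4 = 75.0% (28.4–97.2) | 1/4 = 25.0 points |

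The documents do not say how many infants will have a baseline pathogen, so the smaller denominators are assumptions.

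**The case against.** **The two statements may mean the same thing.** Clinical outcome is assessed only at EOT and TOC. Protocol 8.4.1.1 carries forward failure at EOT, and section 3.9.1.2 equates the day of discontinuation for lack of effect with EOT. On that view, a failure before TOC is simply a failure at EOT, and the text is the programmed form of the footnote. This is a fair reading, and it stands to this extent: a reader might infer a flat contradiction, and the documents do not establish one. But the footnote does not say EOT, and the narrow reading leaves failures between the visits with no rule except the TOC-window culture. The sterile culture under another drug then still counts as eradication.

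**The text already handles most such infants.** With no TOC-window culture, "if clinical failure, the microbiological outcome will be presumed persistence". A positive culture in the window also makes the patient unfavourable. This stands in full. A reader might infer that every infant who relapses and is sterilised by another drug scores as favourable; the text does not say that.

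**A sterile TOC culture is not what the schedule leads one to expect.** Protocol 4.3.1.3 limits infants already assessed as failures to safety assessments at TOC, and cultures are not among them. Repeat cultures stop once sterile, which may be before day 8. SAP section 3 also uses nominal visits, so it is unclear whether an unscheduled culture would count as TOC. This stands too: the route needs a standard-of-care culture that falls in the window. It remains open because the same protocol section asks for repeat cultures after a positive result.

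**Eradication in Table 7 means absence of the pathogen, whatever else was given.** True. The rule proposed below on cultures after another antibacterial is therefore an addition, not a restatement of existing text.

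**The endpoint is secondary and descriptive, and all responses are listed by patient.** Correct. It limits the weight of the point, but a listing does not decide which score enters the rate.

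**Conclusion.** The point holds as a gap in scope with a possible misclassification. The derivation text in SAP 3.2.1.2 is narrower in wording than footnote a in both documents. It allows a favourable microbiological score for an infant who failed clinically and became sterile on a non-study drug.

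Four conditions must all be met: no failure at EOT; a relapse before TOC with a positive culture or none; a non-study antibacterial started; and only sterile cultures counted in the TOC window. The documents do not show how often this would happen, and they do not support calling it the usual course.

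If it happens once, the favourable rate moves by 4.2 points with 24 infants in the denominator and by 12.5 points with 8, where the lower Jeffreys limit goes from 54.6% to 73.8%. These sizes assume that all other infants are favourable. The wording should be settled before analysis because the result otherwise depends on which statement is programmed. The primary safety objective is not affected.

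**What to change.** In SAP 3.2.1.2, bring the derivation text into line with footnote a, for both the per-pathogen and the per-patient response:

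1. Extend carry-forward to patients who become clinical failures between EOT and TOC. Identify them by a TOC clinical response of failure together with a non-study antibacterial started for LOS after EOT and before the TOC culture.
2. Score them from the culture at the time of failure, or as presumed persistence if there is none, and carry that score to TOC.
3. State that a culture taken after that antibacterial was started does not override this score.
4. State whether an unscheduled culture between days 8 and 15 counts as a TOC culture when nominal visits are used.

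This concerns scoring only and changes nothing in patient care.

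The cost is one small added derivation. Because no clinical outcome is scheduled between the visits, the date of failure has to be derived from culture and medication dates. Antimicrobials are recorded under Protocol 7.7, and SAP 3.3.1.3 lists culture collection dates among the baseline variables; I assume later cultures are recorded in the same way. The SAP does not list the reason for a medication as a variable, so check that the CRF shows an antibacterial was started for LOS.

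The favourable rate may be slightly lower. In an infant whose culture at failure was sterile, the aligned rule gives eradication where the present text may give persistence or presumed persistence, so the SAP should name that case explicitly.
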